10.1.2.2. Laboratory data

Missing laboratory results (including immunological data) will not be replaced.

10.1.2.3. Daily recording of solicited symptoms

10.1.2.3.1. Studies with paper diaries

For studies using paper diaries which have questions in the CRF indicating the presence or absence of solicited symptoms, the following rules are applicable.

Denominators for the summary of local (or general) solicited symptoms will be calculated using the number of subjects who respond “Yes” or “No” to the question concerning the occurrence of local (or general) symptoms.

When a specific symptom is marked as having not occurred following a specific vaccination (i.e. SDTM CE.CEOCCUR=N for the specified post-vaccination period for the symptom in question), all daily measurements will be imputed as Grade 0.

When a specific symptom is marked as having occurred following a specific vaccination (i.e. SDTM CE.CEOCCUR=Y for the specified post-vaccination period for the symptom in question), any missing daily recordings will be given imputed values to allow them to contribute to the ‘Any’ rows but not to specific grade rows of the symptom summary tables.

When the occurrence of a specific symptom is not present (i.e. SDTM CE.CEOCCUR is neither Y nor N for the specified post-vaccination period for the symptom in question) but the group of symptoms (local or general) is marked as having occurred (i.e. SDTM CE.CEOCCUR=Y), all missing daily recordings will be given imputed values to allow them to contribute to the ‘Any’ rows but not to specific grade rows of the symptom summary tables.

The following table shows how subjects contribute to each category for a specific solicited symptom over the Day X to Day Y post-vaccination period:

Solicited symptom category	Subjects included in the calculation of the numerator
Any	All subjects with at least one occurrence of the symptom at grade 1, grade 2, or grade 3 between Day X and Day Y or with the symptom marked as present and at least one missing daily recording between Day X and Day Y
At least grade 1	All subjects with at least one occurrence of the symptom at grade 1, grade 2, or grade 3 between Day X and Day Y
At least grade 2	All subjects with at least one occurrence of the symptom at grade 2 or grade 3 between Day X and Day Y
At least grade 3	All subjects with at least one occurrence of the symptom at grade 3 between Day X and Day Y

10.1.2.4. Unsolicited adverse events

Missing severity, relationship with study vaccine, and outcome of unsolicited adverse events will not be replaced and will appear as 'UNKNOWN' in all statistical output.

10.1.3. Data derivation

10.1.3.1. Age at vaccination in days

When age at vaccination is to be displayed in days, it will be calculated as:

Age = date of vaccination minus date of birth

10.1.3.2. Age at vaccination in months

When age at vaccination is to be displayed in months, it will be calculated as the number of complete calendar months between the date of birth (DOB) and the date of vaccination. For example:

DOB = 10JUN2017, Date of vaccination = 09JUL2018 -> Age = 12 months

DOB = 10JUN2017, Date of vaccination = 10JUL2018 -> Age = 13 months

10.1.3.3. Age at vaccination in years

When age at vaccination is to be displayed in years, it will be calculated as the number of complete calendar years between the date of birth and the date of vaccination. For example:

DOB = 10SEP1983, Date of vaccination = 09SEP2018 -> Age = 34 years

DOB = 10SEP1983, Date of vaccination = 10SEP2018 -> Age = 35 years

10.1.3.4. Weight

Weight will be presented in kilograms. Weights reported in pounds will be converted as follows:

$$\text{Weight in kilograms} = \text{Weight in pounds} / 2.2$$

10.1.3.5. Height

Height will be presented in centimeters. Heights reported in feet and inches will be converted as follows:

$$\text{Height in centimeters} = \text{Height in inches} \times 2.54$$

10.1.3.6. Body mass index (BMI)

BMI will be calculated as follows:

$$\text{BMI} = (\text{Weight in kilograms}) / (\text{Height in meters})^2$$

10.1.3.7. Temperature

Temperatures will be presented in degrees Celsius (°C). Temperatures reported in degrees Fahrenheit (°F) will be converted as follows:

$$\text{Temperature (Celsius)} = ((\text{Temperature (Fahrenheit)} - 32) \times 5)/9$$

10.1.3.8. Numerical serology results

Numerical serology results will be derived from the content of IS.ISORRES in the SDTM dataset. For assays with a specific cut-off, the following derivation rules apply:

IS.ISORRES	Derived value
“value” and value is \geq cut-off	value
“value” and value is $<$ cut-off	cut-off/2
“value” and value is $>$ ULOQ (applicable for RSV neutralizing assay)	ULOQ
“value” and value is $<$ LLOQ (applicable for RSV neutralizing assay)	LLOQ/2
value” and value is \geq LLOQ and $<$ ULOQ (applicable for RSV neutralizing assay)	value
All other cases	missing

10.1.3.9. Geometric mean titers (GMTs) and concentrations (GMCs)

Geometric Mean Titer (GMT) or Concentration (GMC) calculations are performed by taking the inverse logarithm of the mean of the log titer or concentration transformations. Antibody titers or concentrations below the cut-off of the assay will be given an arbitrary value of half the cut-off of the assay for the purpose of GMT/GMC calculation. The cut-off value is defined by the laboratory before the analysis and is described in the protocol.

10.1.3.10. Onset day

The onset day for an event (e.g. AE, medication, vaccination) is the number of days between the last study vaccination and the start date of the event. This is 1 for an event occurring on the same day as a vaccination (and reported as starting after vaccination).

10.1.3.11. Duration of events

The duration of an event with a start and end date will be the number of days between the start and end dates plus one day, i.e. an event that starts on 03MAR2018 and ends on 12MAR2018 has a duration of 10 days.

The duration of solicited events will be calculated as the sum of the individual days with the symptom reported at grade 1 or higher.

10.1.3.12. Counting rules for combining solicited and unsolicited adverse events

For output combining solicited and unsolicited adverse events, all serious adverse events will be considered general events since the administration site flag is not included in the expedited adverse event CRF pages.

Multiple events with the same preferred term which start on the same day are counted as only one occurrence.

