*Any safety, immunogenicity and disease surveillance data collected beyond Visit 5 (Day 61) will be collected in Epoch 003. Any safety, immunogenicity and disease surveillance data collected beyond Visit 7 (end of the first RSV transmission season) will be collected in Epoch 004. Refer to the SPM for RSV transmission seasons per country.

- Primary Completion Date (PCD): Visit 5 (Day 61).

- End of Study (EoS): Last testing results released of samples collected at Visit 8 (end of the second RSV transmission season) related to primary and secondary endpoints.*

* Up to Visit 8 (end of the second RSV season), there will be monthly nasal swab to detect asymptomatic RSV infections during the RSV season *or* if following active or a passive surveillance contacts, a subject presents symptoms of respiratory tract infection (RTI), a nasal swab will be collected.

- Study groups:

Table 2 Study groups and epochs foreseen in the study

Study groups	Target Number of subjects	Age (Min/Max)	Epochs			
			Epoch 001	Epoch 002	Epoch 003	Epoch 004
1D RSV + Bexsero	50	6 – 7 months	N/A	x	x	x
1D RSV + Nimenrix		6 – 7 months	N/A	x	x	x
1D RSV + Synflorix		6 – 7 months	N/A	x	x	x
1D RSV + Menveo		6 – 7 months	N/A	x	x	x
1D RSV + Placebo		6 – 7 months	N/A	x	x	x
2D RSV + Bexsero	50	6 – 7 months	N/A	x	x	x
2D RSV + Nimenrix		6 – 7 months	N/A	x	x	x
2D RSV + Synflorix		6 – 7 months	N/A	x	x	x
2D RSV + Menveo		6 – 7 months	N/A	x	x	x
2D RSV + Placebo		6 – 7 months	N/A	x	x	x
Bexsero	50	6 – 7 months	N/A	x	x	x
Nimenrix		6 – 7 months	N/A	x	x	x
Synflorix		6 – 7 months	N/A	x	x	x
Menveo		6 – 7 months	N/A	x	x	x
Placebo		6 – 7 months	N/A	x	x	x

1D: 1 Dose (1.5×10^{10} vp/dose); **RSV:** ChAd155-RSV vaccine; **2D:** 2 Dose (5×10^{10} vp/dose); **N/A:** Not Applicable.

Table 3 Study groups and treatment foreseen in the study

Treatment name	1D RSV ChAd	2D RSV ChAd	Bexsero	Nimenrix	Synflorix	Menveo	FB
Vaccine/ Product name	1D ChAd155-RSV 1.5X10 ¹⁰ vp/dose	2D ChAd155-RSV 5X10 ¹⁰ vp/dose	Bexsero	Nimenrix	Synflorix	Menveo	FB
Study Groups							
1D RSV + Bexsero	x		x				x
1D RSV + Nimenrix	x			x			x
1D RSV + Synflorix	x				x		x
1D RSV + Menveo	x					x	x
1D RSV + Placebo	x						x
2D RSV + Bexsero		x	x				
2D RSV + Nimenrix		x		x			
2D RSV + Synflorix		x			x		
2D RSV + Menveo		x				x	
2D RSV + Placebo		x					
Bexsero			x				x
Nimenrix				x			x
Synflorix					x		x
Menveo						x	x
Placebo							x

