3.2. Endpoints

3.2.1. Primary endpoints

- Occurrence of adverse events (AEs) from first vaccination (Day 1) up to Day 61
 - Occurrence of each solicited local and general AE, during a 7-day follow-up period after each vaccination (i.e., the day of vaccination and 6 subsequent days)
 - Occurrence of any unsolicited AE, during a 30-day follow-up period after each vaccination (i.e., the day of vaccination and 29 subsequent days)
 - Occurrence of any serious adverse event (SAE) from Day 1 up to Day 61
 - Occurrence of episode of spontaneous or excessive bleeding (AE of special interest), during a 30-day follow-up period after each vaccination

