5.3. Analysis of safety and reactogenicity

5.3.1. Analysis of safety and reactogenicity planned in the protocol

5.3.1.1. Within groups assessment

The safety will be descriptively summarized based on the ES. The analysis of local AEs, general AEs and fever will be reported for each RSV + comparator vaccine group and each active control comparator group and also for the pooled RSV vaccine and pooled comparator groups. For the analysis of SAEs and AE of specific interest, the analysis will be performed only on the pooled RSV and pooled comparator groups.

The percentage of subjects with at least one local AE (solicited and unsolicited), with at least one general AE (solicited and unsolicited) and with any AE during the 7-day or 30-day follow-up period will be tabulated with exact 95% confidence interval (CI) after each vaccine dose and overall. The percentage of doses followed by at least one local AE (solicited and unsolicited), by at least one general AE (solicited and unsolicited) and by any AE during the 7-day or 30-day follow-up period will be tabulated, overall vaccination course, with exact 95% CI. The same computations will be done for Grade 3 AEs, for any AEs considered related to vaccination for any Grade 3 AEs considered related to vaccination and AEs resulting in a medically attended visit.

The percentage of subjects reporting each individual solicited local AE (any grade, Grade 2, Grade 3, resulting in a medically attended visit) and solicited general AE (any grade, Grade 2, Grade 3, any related, Grade 2 related, Grade 3 related, resulting in medically attended visit) during the 7-day follow-up period (Day 1-7) will be tabulated for each

RSV + comparator vaccine group and each active control comparator group and also for the pooled RSV vaccine and pooled comparator groups after each vaccine dose and overall. Similarly, the percentage of doses followed by each individual solicited local and general AE and their sub-categories, will be tabulated, overall vaccination course, with exact 95% CI.

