tongue haematoma	10043959
uterine haematoma	10063875
vaccination site haematoma	10069472
vaginal haematoma	10046909
vitreous haematoma	10071936
vulval haematoma	10047756

HAEMORRHAGE

Preferred term	PT code
abdominal wall haemorrhage	10067788
acute haemorrhagic conjunctivitis	10067817
administration site haemorrhage	10075101
adrenal haemorrhage	10001361
anal haemorrhage	10049555
anastomotic haemorrhage	10056346
angina bullosa haemorrhagica	10064223
application site haemorrhage	10072694
arterial haemorrhage	10060964
basal ganglia haemorrhage	10067057
bone marrow haemorrhage	10073581
brain stem haemorrhage	10006145
brain stem microhaemorrhage	10071205
breast haemorrhage	10006254
bronchial haemorrhage	10065739
catheter site haemorrhage	10051099
central nervous system haemorrhage	10072043
cerebellar haemorrhage	10008030
cerebellar microhaemorrhage	10071206
cerebral haemorrhage	10008111
cerebral microhaemorrhage	10067277
cervix haemorrhage uterine	10050022
ciliary body haemorrhage	10057417
conjunctival haemorrhage	10010719
diverticulitis intestinal haemorrhagic	10013541
diverticulum intestinal haemorrhagic	10013560
duodenitis haemorrhagic	10013865
ear haemorrhage	10014009
encephalitis haemorrhagic	10014589
gastric haemorrhage	10017788
gastroduodenal haemorrhage	10053768
gastrointestinal haemorrhage	10017955
genital haemorrhage	10061178
haemarthrosis	10018829
haematemesis	10018830
haematochezia	10018836
haematotympanum	10063013
Haematuria	10018867
haemorrhage	10055798
haemorrhage coronary artery	10055803

Preferred term	PT code
haemorrhage intracranial	10018985
haemorrhage subcutaneous	10018999
haemorrhage subepidermal	10019001
haemorrhage urinary tract	10055847
haemorrhagic anaemia	10052293
haemorrhagic diathesis	10062713
haemorrhagic disorder	10019009
haemorrhagic infarction	10019013
haemorrhagic ovarian cyst	10060781
haemorrhagic pneumonia	10077933
haemorrhagic thyroid cyst	10072256
haemorrhagic urticaria	10059499
injection site haemorrhage	10022067
internal haemorrhage	10075192
intestinal haemorrhage	10059175
intra-abdominal haemorrhage	10061249
intraventricular haemorrhage	10022840
iris haemorrhage	10057418
joint microhaemorrhage	10077666
lacrimal haemorrhage	10069930
large intestinal haemorrhage	10052534
laryngeal haemorrhage	10065740
lip haemorrhage	10049297
lower gastrointestinal haemorrhage	10050953
lymph node haemorrhage	10074270
mediastinal haemorrhage	10056343
mesenteric haemorrhage	10060717
mouth haemorrhage	10028024

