10.1.3.19. Statistical methodology

10.1.3.20. Exact confidence intervals around proportions

The exact confidence intervals around within-group proportions are derived using the method of Clopper and Pearson [Clopper, 1934].

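### In the combined solicited-plus-unsolicited table only, a serious injection-site reaction is counted as general instead of local, and the table carries no note of this

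*SAP*

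**What the plan says.** SAP section 10.1.3.12 sets a rule whose scope is output combining solicited and unsolicited events, and gives the absence of a site flag on the form as its reason: "all serious adverse events will be considered general events since the administration site flag is not included in the expedited adverse event CRF pages".

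The output concerned is planned in section 5.3.1.1: "The percentage of subjects with at least one local AE (solicited and unsolicited), with at least one general AE (solicited and unsolicited"). Any-event percentages are planned beside these, over 7 and 30 days, after each dose and overall, with exact 95% intervals. The same computations follow for Grade 3, related, Grade 3 related and medically attended events. Template 15 is the shell, with one row each for any, local and general events. Its footnotes define the denominators and the interval, but do not say how serious events are classed.

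Section 9.4 lists the preferred terms for events of specific interest. Several carry the site in the term, for example "vaccination site haematoma", with parallel injection-site and administration-site terms for haematoma and for haemorrhage.

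**The concern.** A reader of Template 15 will take its local row to mean all local events, solicited or not, serious or not. Under the rule it means non-serious local events plus whatever local reactions the diary captured. The events that move are the most serious local reactions, and the error has one direction: the local row can only be too low and the general row only too high. It would show most in the sparse versions of the table (Grade 3, related, medically attended), where a single infant can be the whole count.

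The missing form flag does not force this choice. Serious events are coded and tabulated by MedDRA preferred term (section 5.3.1.1; Templates 21, 22, 23 and 30), and the SAP already uses term lists to identify events of specific interest (section 9.4). For many serious local reactions the site is therefore in the data without the flag.

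**Working it through.** The SAP gives no figure for this point, so there is none to reproduce. The check has two parts.

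**Which outputs the rule reaches**

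| Output | Source | Changed by the rule? |
|---|---|---|
| Combined table, local row | 5.3.1.1, Template 15 | Yes, can be too low |
| Combined table, general row | 5.3.1.1, Template 15 | Yes, can be too high |
| Combined table, any-event row | 5.3.1.1, Template 15 | No, the infant counts either way |
| Primary endpoints | 3.2.1 | No, none is a combined local-versus-general rate |
| Individual solicited local events | Template 16 | No, taken from diaries |
| SAE tables and listing | Templates 21, 22, 23, 30 | No, there is no local/general split |
| Between-group comparisons | 5.3.1.2 | No, there is no local/general split |
| Combined summary for posting | 5.3.2.1, Template 29 | No, serious events are excluded |

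**Size in the affected rows**

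Inputs: 50 infants per pooled group (Table 2), and Clopper-Pearson intervals (section 10.1.3.20). The SAP gives no expected number of serious local reactions, so one or two per pooled group is an assumption made for illustration.

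- Shift per infant: 1/50 = 2.0 percentage points at most.
- Upper limit for 0/50: 1 − 0.025^(1/50) = 7.1%.
- Upper limit for 1/50: the p that solves (1−p)^50 + 50p(1−p)^49 = 0.025, which is 10.6%.

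| Situation | Local row under the rule | Local row if counted as local |
|---|---|---|
| One such infant, no other local event in the row | 0/50: 0% (0 to 7.1) | 1/50: 2.0% (0.05 to 10.6) |
| Two such infants, no other local event in the row | 0/50: 0% (0 to 7.1) | 2/50: 4.0% (0.5 to 13.7) |
| One such infant, local events common | 24/50: 48.0% (33.7 to 62.6) | 25/50: 50.0% (35.5 to 64.5) |
| Infant already has a qualifying local event | no change | no change |

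The general row rises by at most the same number of infants, and not at all for an infant who already has a qualifying general event.

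**The case against.** The strongest reply is that this is a stated convention with its reason given, that it contradicts nothing else in the SAP, and that it hides no event. A serious injection-site reaction still appears in the any-event row, in the SAE tables by preferred term and in the SAE listing. An injection-site haematoma would also fall under the bleeding events of specific interest, with its own listing (Template 25). All of this stands, and it limits the point to the labelling of two rows in one family of tables.

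A second reply is that preferred terms are an imperfect substitute for a flag. Section 5.3.2.1 codes the solicited local symptoms to Pain, Erythema and Swelling, without a site, so a term can omit the site of a truly local event. Conversely, a site term need not refer to a study injection: the conditions under elimination code 1040 (section 4.2.3.1) allow routine paediatric vaccines from 7 days after a study dose, inside the 30-day window. This also stands. It shows that a term list will misclassify some events, and it is a reason to check the verbatim. It does not favour a rule that classes every serious local event wrongly in this table.

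A reader might infer that the primary safety result is distorted. The documents do not support that. The primary endpoints take each solicited event separately ("Occurrence of each solicited local and general AE, during a 7-day follow-up period after each vaccination"), together with any unsolicited event, any SAE and bleeding episodes, and serious local reactions are not a named endpoint. Nor does the rule lower local rates throughout the report, because it applies only to combined output.

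**Conclusion.** The point holds in a narrow form. In Template 15, including its Grade 3, related and medically attended versions, a serious injection-site reaction reported on the expedited pages counts as general and not local, and the table does not tell the reader.

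The size is at most 2 percentage points per infant in a pooled group of 50, and the local row does not move if the infant has another qualifying local event. That last statement assumes that a diary record keeps its local class. Section 10.1.3.12 merges events with the same preferred term and start day into one occurrence, but does not say which class a reaction recorded both in the diary and on the expedited page would take.

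A larger percentage for the by-comparator groups would need their sizes. Table 2 gives targets only for the pooled groups, and the comparator is chosen by country, so an even spread cannot be assumed. Because such events should be rare, the rule may change nothing in practice. This is a small improvement worth making, not a threat to the trial's conclusions.

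**What to change.** Replace the rule in section 10.1.3.12 with one along these lines: in combined output, a serious event with an injection-site, vaccination-site or administration-site preferred term counts as local, once the verbatim confirms that the site is that of a study injection; all other serious events count as general. Fix the term list before the unblinding at the Day 61 analysis (section 7.1), so that no classification is made with treatment known. Add a footnote to Template 15 stating the rule.

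The cost is one SAP sentence, a short term list, a footnote and a verbatim check on what should be very few events. No form change is needed. The downside is that a term can omit the site, so some misclassification may remain; the footnote should say so.

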10.1.3.13. Counting rules for occurrences of solicited adverse events

When the occurrences of solicited adverse events are summarized, each event recorded as having occurred during a specific period will be counted as only one occurrence regardless of the number of days on which it occurs. Also, in the case of co-administered study vaccines, an injection site reaction recorded for a subject following multiple vaccines will be counted as only one occurrence.

10.1.3.14. Display of decimals**10.1.3.15. Percentages**

Percentages and their corresponding confidence limits will be displayed with:

- no decimals when there are fewer than 50 subjects in each tabulated group
- one decimal when there are at least 50 subjects in at least one tabulated group
 - Exceptions will be made for percentages that are not 0% or 100% but appear as 0% or 100% due to rounding. For these specific cases the number of decimals will be increased until the displayed value is no longer 0% or 100%. Examples are given in the following table.

n/N	Displayed percentage
10/45	22%
1/45	2%
10/55	18.2%
1/55	1.8%
1/300	0.3%
1/3000	0.03%
1/30000	0.003%
299/300	99.7%
2999/3000	99.97%
29999/30000	99.997%

- The display of additional decimals for values close to 0% or 100% will be applied only to point estimates and not confidence limits, which can be rounded and displayed as 0% or 100%.
- Values of exactly 0% or 100% will be presented with no decimals regardless of the number of subjects per tabulated group.

10.1.3.16. Differences in percentages

Differences in percentages and their corresponding confidence limits will be displayed with one more decimal than the maximum number used to display the individual percentages, for example the difference between two percentages displayed with one decimal will be displayed with two decimals.

10.1.3.17. Demographic/baseline characteristics statistics

The mean, median, and standard deviation for continuous baseline characteristics (height, weight, body mass index (BMI), pre-vaccination body temperature) will be presented with one decimal.

The minimum and maximum values and quartile values (if required) will be presented with the same number of decimals as the observed values.

The maxima and minima of transformed height variables will be displayed with no decimals.

The maxima and minima of transformed weight variables will be displayed with no decimals with the exception of values below 10kg where one decimal will be displayed.

The maximum and minima of transformed body temperatures will be displayed with one decimal.

